**For all participants who have a PICC inserted within 48 hours from randomisation:**

**At PICC removal**, the attending clinical staff/RN will routinely take a PICC tip culture according to standard clinical practice.

A detailed SOP version 1.0 dated 05/03/2015 on handling and culturing premechath line tips will be disseminated to site's microbiology laboratories.

## **8.4 Procedures for Assessing Safety**

Adverse events whose causal relationship to the trial intervention (PICC) is assessed and judged by the investigator to be possibly, probably, or almost certainly related to the intervention that occur at the time from the first attempt of PICC insertion within 48 of randomisation hours until the clinical follow up for primary outcome (see table 1 in section 8.2) should be reported (see section 10.1).

These will be reported as they arise as described in section 10. An independent Data and Safety Monitoring Committee (IDSMC) will be convened to monitor safety data (see section 16.3 for further details).

**Note:** Although this is an unblinded trial all sites are expected to adhere to good practice in terms of treating babies similarly, regardless of the allocated PICC.

## **8.5 Loss to Follow-up**

Trial follow-up is by the trial RN until discharge home from neonatal care, death or 6 months (26 weeks) after randomisation (whichever occurs first). Refer to section 5.3 for further details relating to the process of transferring participants and the prevention of loss to follow-up.

If a participant is lost to follow-up prior to discharge home from neonatal care, all participants will still be followed up at 6 months (26 weeks) post randomisation as detailed in section 17.

## **8.6 Trial Closure**

The end of the trial is defined to be the date on which data for all participants is frozen and data entry privileges are withdrawn from the trial database. However, the trial may be closed prematurely by the Trial Steering Committee (TSC), on the recommendation of the Independent Data and Safety Monitoring Committee (ISDMC).

## 9 STATISTICAL CONSIDERATIONS

### 9.1 Introduction

A separate and full Statistical Analysis Plan (SAP) will be developed prior to the final analysis of the trial. The SAP will be agreed by the Trial Steering Committee (TSC). The main features of these planned statistical analyses are included here in the main protocol.

### 9.2 Method of Randomisation

Participants will be randomised to S-PICC or AM-PICC in a ratio of 1:1. Randomisation lists will be generated using blocks of random length and stratified by NNU. The lists will be produced by an independent statistician (who is not involved with the PREVAIL trial) at the MC CTU.

### 9.3 Outcome Measures

The primary and secondary outcomes are provided in section 4.

### 9.4 Sample Size

When the sample size in each group is 408, with a total number of blood stream infections required of 79, a 0.050 level two-sided log-rank test for equality of survival curves will have 90% power to detect the difference between a proportion of 0.14 and a proportion of 0.07 (a constant hazard ratio of 2.078). Assuming 5% loss to follow up due to transfers, we estimate that 858 babies would need to be randomised (429 to each arm).

The basis of this calculation is as follows:

- i) Baseline event rate: The incidence of BSI in babies less than 32 weeks gestation with PICC was assumed to be 14/1000 CVC days, based on unpublished audits of BSI event rates at 3 hospitals (Table 2). Hospital A shows a recent reduction in BSI which follows a series of hospital infection control initiatives. As other units have not seen major reductions in rates, and recent rates from one unit are as high as 20/1000 CVC days, we have used 14/1000 CVC days for the sample size estimate. In addition, the rates in Table 2 are considered conservative as the denominators include a minority of babies with umbilical venous catheters and surgically inserted venous catheters for which the rate of BSI is lower than for PICC. In addition, the rates of BSI measured in the units reflects all kinds of CVC, and babies for whom Premicath insertion is appropriate may be expected to experience BSI more frequently than typical NNU inpatients.
- ii) Duration of PICC insertion. This was estimated as a median of 10 days, based on an audit of 5 NNUs (with mean duration ranging from 10 to 29 days). Hence the proportion of babies with a BSI in the standard arm is estimated to be 14%.
- iii) A 50% absolute reduction in the event rate. This is conservative when viewed against results of a network meta-analysis by Wang et al (mean odds ratio 0.18 and upper

limit of a 95% confidence interval of 0.34) because of the factors that may attenuate the treatment effect in very preterm babies (see section 2.2).

- iv) A 5% loss to follow is realistic as follow up should be complete for babies remaining on the NNU, but a very small number may be transferred with their PICC in-situ. Efforts will be made to capture primary outcome data for babies transferred to non-participating NNUs.

Table 3 demonstrates the impact on statistical power of the control group event rate variation maintaining the sample size of 408 in each group (prior to adjusting for loss to follow up).

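### Section 9.4 turns a daily BSI rate into a 14% risk by simple multiplication and calls a relative halving absolute, so the stated 90% power does not follow from its stated inputs

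*Protocol*

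**What the plan says.** Protocol section 9.4 gives the design as follows: "When the sample size in each group is 408, with a total number of blood stream infections required of 79", and "a 0.050 level two-sided log-rank test for equality of survival curves will have 90% power". The target is "the difference between a proportion of 0.14 and a proportion of 0.07 (a constant hazard ratio of 2.078"). Allowing for 5% loss, 858 babies are to be randomised.

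Three numbered items supply the basis. Item (i), on the baseline event rate, assumes 14 BSI per 1000 CVC days. Item (ii) gives the time in situ: "This was estimated as a median of 10 days, based on an audit of 5 NNUs (with mean duration ranging from 10 to 29 days"). From these two it concludes: "Hence the proportion of babies with a BSI in the standard arm is estimated to be 14" per cent. Item (iii) states the effect: "A 50% absolute reduction in the event rate".

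Table 3 then varies what it calls the control group rate, in per cent, and halves it in every row. There the word means a proportion of babies, not a rate per day.

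**The concern.** Multiplying 0.014 per day by 10 days gives the expected number of infections per baby when every baby is exposed for 10 days. Section 9.4 enters that number as the proportion of babies infected in a log-rank calculation with constant hazards. The two differ, because under a constant hazard the proportion is 1 − exp(−rate × time).

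Three further points concern the same derivation. A 50% absolute reduction from 14% is impossible. Event rate means infections per 1000 days in item (i) but a proportion in Table 3, so it is unclear which of the two is halved, and the hazard ratio depends on the answer. And rate times median duration is not an expected proportion anyway, because that depends on the whole distribution of dwell times, which is not stated.

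At stake is whether the printed 90% power follows from the printed rate, duration and effect. It matters in practice because section 9.5 asks the IDSMC to review the sample-size parameters at the interim. The committee can be shown BSI per 1000 PICC days (a secondary endpoint in section 4.2) and dwell times, and needs assumptions it can compare them with.

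**Working it through.** **Inputs, all from section 9.4 unless noted.** Control rate 0.014 per day; 10 days (median); reduction 50%; two-sided α 0.05 (z = 1.960); power 90% (z = 1.2816); 408 per arm. (1.960 + 1.2816)² = 10.507.

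**Reproducing the printed design.**
- Hazard ratio: ln(0.86)/ln(0.93) = 2.078, as printed.
- Freedman events: 10.507 × (3.078/1.078)² = 85.6. Divided by 0.14 + 0.07 this gives 407.8, so 408 per arm, as printed.
- Schoenfeld events: 4 × 10.507/(ln 2.078)² = 78.5, so 79, as printed.

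The 408 and the 79 thus come from different formulas. That is a separate matter, which takes 14% and 7% as given.

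**What 14% and 7% imply over 10 days.** −ln(0.86)/10 = 15.1 per 1000 days and −ln(0.93)/10 = 7.3 per 1000 days. The reduction is 1 − 7.26/15.08 = 52%.

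**Converting the stated rate over exactly 10 days.** Control: 1 − exp(−0.14) = 13.1%.
- *Daily rate halved:* 1 − exp(−0.07) = 6.8%, HR 2.0. Events: 408 × (0.1306 + 0.0676) = 80.9. Freedman power: Φ(√80.9 × 1/3 − 1.96) = Φ(1.04) = 85.0%. Schoenfeld power: Φ(½ × ln 2 × √80.9 − 1.96) = Φ(1.16) = 87.6%. A log-rank simulation of 8000 runs gave 85.9%.
- *Proportion halved, as in Table 3:* 6.53%, HR ln(1 − 0.1306)/ln(1 − 0.0653) = 2.072, 80.0 events, power 87.7% (Freedman) or 90.3% (Schoenfeld).

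**Sensitivity to dwell.** The protocol gives no distribution, so the exponential form is my assumption. With mean m days, the proportion infected at daily rate r is r/(r + 1/m). A median of 10 days corresponds to a mean of 10/ln 2 = 14.4 days. The 11-day and 12-day rows reflect the endpoint window in section 4.1 (24 hours after randomisation to 48 hours after removal): a 10-day dwell spans 11 days at risk if the line goes in at randomisation, and 12 if it goes in a day later. Power is Φ(√d × (HR − 1)/(HR + 1) − 1.96) for Freedman and Φ(½ × ln HR × √d − 1.96) for Schoenfeld, where d is the expected number of events at 408 per arm.

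| Assumption | Control | AM-PICC | HR | Events | Freedman | Schoenfeld |
|---|---|---|---|---|---|---|
| Printed proportions | 14.0% | 7.0% | 2.078 | 85.7 | 90.0% | 92.3% |
| Fixed 10 days, rate halved | 13.1% | 6.8% | 2.000 | 80.9 | 85.0% | 87.6% |
| Fixed 10 days, proportion halved | 13.1% | 6.5% | 2.072 | 80.0 | 87.7% | 90.3% |
| Fixed 11 days, rate halved | 14.3% | 7.4% | 2.000 | 88.5 | 88.0% | 90.3% |
| Fixed 12 days, rate halved | 15.5% | 8.1% | 2.000 | 96.0 | 90.4% | 92.4% |
| Exponential, mean 10 days, rate halved | 12.3% | 6.5% | 2.000 | 76.8 | 83.2% | 85.9% |
| Exponential, median 10 days, rate halved | 16.8% | 9.2% | 2.000 | 106.0 | 92.9% | 94.6% |
| Exponential, mean 29 days, rate halved | 28.9% | 16.9% | 2.000 | 186.7 | 99.5% | 99.7% |

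Like for like, fixed 10 days with the rate halved costs about 5 points by either formula (90.0% to 85.0%, or 92.3% to 87.6%). With the proportion halved it costs about 2.

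**The case against.** The strongest reply is that none of this shows the trial to be underpowered. A reader might infer that the stated inputs really give 85% power and that the errors all flatter the design. The protocol does not support that. The 85% needs every line to stay exactly 10 days, whereas 10 days is a median and no audit mean quoted beside it is lower. A right-skewed dwell with median 10 days has a longer mean, which more than offsets the faulty conversion in the exponential case. With HR 2.0 and exponential dwell, a mean of about 12.7 days already restores 90% by Freedman (15.1% and 8.2%, about 95 events). The at-risk window is also longer than the dwell. This part of the objection stands.

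It also stands that 2.078 is the correct hazard ratio for 14% and 7%. Table 3 halves proportions under the name of rate, so item (iii) may mean the same. The hazard ratio is wrong only if the daily rate is halved, which is the sense event rate carries in item (i). The wording permits both readings.

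Finally, the gap between 13.1% and 14% is small beside audit rates of 4.8 to 20.0 per 1000 days in Table 2, section 9.4 calls those rates conservative, and Table 3 already shows 77% power at a 10% control proportion. That limits the practical weight of the point. It does not make the derivation valid: the step to 14% is wrong on any reading, and so is the label absolute.

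**Conclusion.** The point holds as a fault in the derivation, not as a finding that power is too low. Two things are wrong whatever one assumes: rate times median duration is presented as a cumulative risk, and a relative halving is called absolute. Two things are left open that determine the power: whether the daily rate or the proportion is halved, and how long lines stay in.

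If every line stays exactly 10 days, the stated rate gives a 13.1% control risk and, at 408 per arm, power of about 85% to 88% with the rate halved or about 88% to 90% with the proportion halved. Under the exponential dwell assumption with the rate halved, Freedman power runs from about 83% (mean 10 days) through 93% (median 10 days) to over 99% (mean 29 days). The net direction of the error therefore cannot be read from the protocol. What can be said is that the printed 90% does not follow from the printed inputs, and that over 10 days the powered proportions correspond to 15.1 vs 7.3 per 1000 days, not 14 vs 7.

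**What to change.** Keep 858 babies and restate section 9.4:

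- Replace *absolute* with *relative* in item (iii), and say whether the daily rate or the proportion is halved.
- Replace the step to 14% with a valid conversion under a stated dwell assumption. For example: if every PICC stays 10 days and the daily rate falls from 14 to 7 per 1000 days (hazard ratio 2.0), 13.1% vs 6.8% of babies have a BSI, about 81 events are expected at 408 per arm, and power is about 85% (Freedman) to 88% (Schoenfeld). Alternatively, keep 14%, 7% and 2.078, and state that over 10 days they correspond to 15.1 vs 7.3 per 1000 days.
- Give power across the audit's range of dwell times, naming the distribution assumed, so that the IDSMC can set observed rates and dwell times against the design.

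The cost is text in one section, with no extra babies. The downside is that, under a fixed 10-day dwell, the stated power becomes slightly less favourable.

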**Table 2: BSI rate (any positive culture) for babies born at <32 weeks of gestation per central venous catheter days**

Site	Audit period	BSI/1000 CVC days
Hospital A	2007-2010	14.3 (160/11166)
Hospital A	2011	7.2 (21/2898)
Hospital A	2012	4.8 (13/2713)
Hospital B	Jan-June 2013	10.8 (9/833)
Hospital C	July 2012-July 2013	20.0 (28/1398)

**Table 3: Power to detect an effect given different control group rates of BSI**

Control group rate (%)	Impregnated line group rate (%)	Power (%)	Number of events
5	2.5	46	28
10	5	77	56
15	7.5	90	79
20	10	97	112

## 9.5 Interim Monitoring and Analyses

The trial will be monitored by an Independent Data and Safety Monitoring Committee (IDSMC) who will assess the trial data and take into account the current world-wide evidence. The IDSMC members will comply with a trial-specific IDSMC charter according to International Conference on Harmonisation Good Clinical Practice (ICH GCP) guidelines.

The trial statistician at the MC CTU will prepare the report for the IDSMC, the contents of which will be agreed by the IDSMC. The IDSMC will be asked to give advice on whether the accumulated data from the trial, together with results from other relevant trials, justifies continuing recruitment of further patients or further follow-up. A decision to discontinue recruitment, in all patients or in selected subgroups will be made only if the result is likely to convince a broad range of clinicians including participants in the trial and the general clinical community. If a decision is made to continue, the IDSMC will advise on the frequency of future reviews of the data on the basis of accrual and event rates. The IDSMC will make recommendations to the Trial Steering Committee (TSC, see section 16) as to the continuation of the trial.

There will be an interim analysis of the primary outcome half-way through the trial (when approximately half of the participants have been randomised), using Peto-Haybittle stopping rules. A full statistical analysis plan will be written prior to any comparison of the treatment groups. At this point the Independent Data and Safety Monitoring Committee (IDSMC) will make a recommendation to the TSC for the trial to continue or stop. Statistical significance

alone will not stop the trial; a decision to discontinue recruitment will be made only if the result is likely to convince a broad range of clinicians including participants in the trial and the general clinical community or if there are safety issues. The IDSMC will also review the parameters used within the sample size calculation at this time.

## **9.6 Analysis Plan**

The trial will be analysed using the International Conference on Harmonisation E9 guidelines and reported using the 'Consolidation Standard of Reporting Trials' (CONSORT) guidelines. A full and detailed statistical analysis plan will be developed prior to the final analysis of the trial. The main features of the statistical analysis plan are included here.

The analysis of primary and secondary outcomes will use the principle of intention to treat, based on all the randomised participants, as far as is practically possible. Per protocol sensitivity analyses will also be carried out on a number of outcomes, these will be specified in the statistical analysis plan. A p-value of 0.05 or less will be used to declare statistical significance for all analyses and results will be presented with 95% confidence intervals. Baseline characteristics will be presented but no comparisons will be undertaken, rather the clinical importance of any imbalance will be noted.

Kaplan-Meier survival curves and log rank tests will be used for time to event outcomes including the primary outcome 'time to first BSI'. Continuous data will be presented as means and standard deviations and analysed using two-sample tests (if data is skewed, medians and ranges will be presented and analysis will be by Mann Whitney U tests). Binary data will be reported in terms of relative risk and analysed using chi-squared or Fisher's exact tests as appropriate.

All related adverse events (AEs) and related serious adverse events (SAEs) reported by the clinical investigator will be presented, identified by treatment group, but no formal comparisons will be made across the treatment groups.

Missing data will be monitored and strategies developed to minimise its occurrence, however as much data as possible will be collected about the reasons for missing data and this will be used to inform the handling of missing data.

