## 4 TRIAL DESIGN

### 4.1 Primary Endpoint

The primary endpoint will be time to first BSI based on a positive blood/CSF culture (any positive bacterial or fungal blood/CSF culture will be included) taken between 24 hours after randomisation until 48 hours after removal.

As part of the primary endpoint there will be two sensitivity analyses:

1. A sensitivity analysis confined to clinically serious BSI defined by positive culture and the baby is treated for more than 72 hours with intravenous antibiotics or dies during treatment.
2. Time to first BSI based on a positive blood culture (including fungal BSI) taken between 24 hours after PICC insertion until 48 hours after removal.

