### 4.2 Secondary Endpoint(s)

Outcomes captured up until 48 hours after PICC removal:

1. Rifampicin resistance in any isolate from blood/CSF culture.
2. Rifampicin resistance in any isolate from PICC tips.
3. Type of organism isolated from BSI.
4. Rate of BSI per 1000 PICC-days (including recurrent BSI).
5. Occurrence of 1 or more BSI.
6. Rate of catheter-related BSI per 1000 PICC days.
7. Rate of blood/CSF culture sampling per 1000 PICC days.
8. Duration of antimicrobial exposure from randomisation up to 48 hours after line removal.
9. Time to PICC removal.

Outcomes captured up until discharge home from neonatal care/death/6 months post randomisation:

10. Chronic lung disease 36 weeks postmenstrual age.
11. Necrotizing enterocolitis (NEC): Bell's stage II or III.
12. Treatment for retinopathy of prematurity.
13. Abnormalities on cranial ultrasound.
14. Time to full milk feeds after randomisation.
15. Total duration of parenteral nutrition from randomisation until discharge from NNU.
16. Death:
  - a) within 6 months (26 weeks) of randomisation
  - b) before discharge home from neonatal care
  - c) Time to death

For health economics outcomes, please refer to Part II: Economic Analysis.

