## 8.2 Clinical Follow-up for Primary Outcome

**Table 1: Definitions of Clinical Follow-up for Primary Outcome**

Situation:		Clinical follow-up for primary outcome will continue until 48 hours after:
Type of PICC used for attempted insertion within 48 hours from randomisation	Type of PICC inserted within 48 hours from randomisation	
Allocated PICC	Allocated PICC	Allocated PICC removed
Allocated PICC	Non-allocated PICC	Non-allocated PICC removed
Allocated PICC and non-allocated PICC	None	Last attempted insertion of allocated PICC
Allocated PICC	None	Last attempted insertion of allocated PICC
Non-allocated PICC	Non-allocated PICC	Non-allocated PICC removed
Non-allocated PICC	None	Last attempted insertion of non-allocated PICC
None	None	Randomisation

**Note:** ‘Allocated PICC’ refers to the type of PICC allocated to the participant during the randomisation process. Whether the allocated PICC or a non-allocated PICC was inserted within 48 hours of randomisation, the inserted PICC will be referred to hereafter as the ‘Randomised PICC’.

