## 8.3 Procedures for Assessing Efficacy

For all participants from the time of randomisation until the clinical follow up for primary outcome (see table 1 in section 8.2).

**When clinically indicated, blood/CSF culture samples** will be taken. It will be the responsibility of the clinician to decide when blood/CSF culture samples need to be taken. The RN will monitor blood/CSF culture sampling and ensure that the PICC tip is sent for culture at removal. The RN will be responsible for recording the culture results and resistance profiles on Form 5: Microbiology.

Blood for blood cultures is best taken prior to commencing antibiotics. However, it is still worth taking blood cultures even if already on antibiotics if there is a clinical indication.

A minimum of 0.5ml should be taken from a new peripheral site (e.g. new peripheral line or closed blood culture system).

The primary outcome will be based on any clinically indicated positive blood culture taken between 24 hours after randomisation to 48 hours after PICC removal. Information on factors contributing to death should be considered a clinical indication for blood/CSF culture sampling, when factors leading to death are uncertain. Blood/CSF cultures should be taken

before death in babies who are deteriorating as blood/CSF cultures taken after death may be a consequence rather than a cause of death and will not be included in the primary outcome.

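### The Kaplan-Meier display for time to first BSI overstates the proportion of babies infected, because most babies leave the risk set through line removal; cumulative incidence curves should be shown beside the log-rank test

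*Protocol*

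**What the plan says.** Protocol section 9.6 presents the main features of the analysis and applies one rule to every time-to-event outcome: "Kaplan-Meier survival curves and log rank tests will be used for time to event outcomes". It names time to first BSI explicitly. No competing-event method is mentioned.

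Section 4.1 counts cultures "taken between 24 hours after randomisation until 48 hours after removal" of the line. Table 1 in section 8.2 fixes the end of observation in the same way ("Clinical follow-up for primary outcome will continue until" 48 hours after removal, or after the last attempted insertion or randomisation if no line was placed). Section 8.3 adds that cultures taken after death "will not be included in the primary outcome", so death also ends observation.

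Section 9.4 sizes the trial on proportions: "Hence the proportion of babies with a BSI in the standard arm is estimated to be 14" per cent, against 7% with the impregnated line, tested by log-rank.

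Section 4.2 lists as secondary endpoints the occurrence of one or more BSI, the BSI rate per 1000 PICC-days, time to PICC removal, and "Time to full milk feeds after randomisation". Section 9.6 reports binary outcomes as relative risks.

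**The concern.** The protocol nowhere uses the word censoring, but the rule follows from what it fixes. A Kaplan-Meier estimate with no competing-event method, applied to follow-up that stops 48 hours after removal or at death, censors babies at those points. Removal is the usual way out of the risk set, not occasional loss. One minus Kaplan-Meier then describes a setting in which no line is ever removed and no baby dies. Its vertical axis will nevertheless be read as the percentage of babies infected.

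Section 5.4 lists infection among the clinical reasons for removing a line, so removal cannot be assumed independent of BSI either.

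Two things are at stake. The main figure would show BSI risks well above the proportion infected given elsewhere in the same report. Also, the log-rank test compares hazards while the line is in place, and that comparison need not agree with the comparison of proportions infected if lines stay in longer in one arm.

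The same blanket rule covers time to full milk feeds. A baby who dies before full feeds can never reach them, yet censoring at death treats that baby as still able to.

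**Working it through.** **The plan's own figures.** Section 9.4 obtains the control proportion as 14/1000 per day × 10 days = 0.14. The hazard ratio is ln(0.86)/ln(0.93) = 2.078, as stated. The events needed are 4 × (1.960 + 1.282)² / (ln 2.078)² = 78.5, so 79, as stated. None of these changes below.

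**Inputs.**
- BSI hazard λ = 0.014 per day (section 9.4).
- Median dwell 10 days (section 9.4). Exponential shape is an assumption, giving a removal hazard μ = ln 2/10 = 0.0693.
- Observation continues 2 days after removal (section 4.1).
- Simplifications: constant BSI hazard, removal independent of BSI, the initial 24-hour exclusion and the delay to insertion ignored, and deaths not modelled (the protocol gives no death rate during line dwell).

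**Formulas.**
- One minus Kaplan-Meier at day t: 1 − exp(−λt).
- Cumulative incidence at day t (t > 2), with end of line exposure competing: [1 − exp(−2λ)] + λ/(λ+μ) × exp(2μ) × [exp(−2(λ+μ)) − exp(−(λ+μ)t)].
- With the numbers in: 0.0276 + 0.1680 × 1.1487 × [0.8465 − exp(−0.0833t)].

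| Day | 1 − KM | Cumulative incidence | Ratio |
|---|---|---|---|
| 10 | 13.1% | 10.7% | 1.22 |
| 20 | 24.4% | 15.5% | 1.58 |
| 30 | 34.3% | 17.5% | 1.96 |

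If t is allowed to run on, the cumulative incidence levels off at 0.0276 + 0.1680 × 1.1487 × 0.8465 = 19.1%. About 81% of babies therefore leave without a BSI. At day 30 the share still at risk is exp(−0.014 × 30) × exp(−0.0693 × 28) = 9.4%, so the widest gap sits where the curve is least precise.

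**Sensitivity to dwell.** Section 9.4 quotes mean dwell from 10 to 29 days across the audited units. With the same formula at day 30:
- Mean 10 days (μ = 0.1): 0.0276 + 0.1228 × 1.2214 × (0.7961 − 0.0327) = 14.2%, ratio 34.3/14.2 = 2.4.
- Mean 29 days (μ = 0.0345): 0.0276 + 0.2888 × 1.0714 × (0.9076 − 0.2335) = 23.6%, ratio 34.3/23.6 = 1.5.

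With less variable (gamma) dwell of median 10 days and the tail ignored, the day-10 ratio is only 1.05 to 1.26. The direction is constant; the size is not.

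**Hazard against proportion.** Ignoring the tail, the proportion ever infected is λ/(λ+μ). If the BSI hazard is multiplied by HR and dwell by 1/HR, both hazards scale together and the proportion stays at 0.014/0.0833 = 16.8%. In simulated trials of 408 per arm, HR 0.70 with dwell 1.43 times as long gave a significant log-rank benefit in 54% of trials, although the proportions infected were equal. With equal dwell and the design hazard ratio (1/2.078 = 0.481), the proportions are 16.8% and 0.00674/(0.00674 + 0.0693) ≈ 8.9%, so the benefit shows on both scales.

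**The case against.** The strongest reply is that the primary test is sound. The log-rank test is valid for the cause-specific hazard, and for a device whose effect operates during exposure that is a defensible target. The occurrence of one or more BSI and time to PICC removal are both planned comparisons, so a divergence between hazard and proportion would be visible in the report. This stands, and it limits the point to the display and its interpretation.

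A second reply is that censoring rules and plotting horizons belong in the SAP. This stands in part: the SAP may refine the rule. But section 9.6 does not leave the method open. It names Kaplan-Meier for this outcome, and following that text gives the wrong curve for risk.

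Three stronger readings are tempting, and the documents do not support them.

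- A reader might infer that the curve doubles the true risk. The ratio is 1.22 at day 10 and nears 2 only around day 30 under the assumed dwell. The protocol gives no horizon.
- A reader might infer a mismatch with the 14% v 7% design. One minus Kaplan-Meier at day 10 is 13.1%, close to 14%, while the cumulative incidence is 10.7% at day 10 and 19.1% eventually, so neither curve clearly fits better.
- A reader might infer that a log-rank benefit with no fewer infected babies is to be expected. That needs dwell on the impregnated line to lengthen by about 1/HR, or 2.08 times at the design effect. The unblinded design and removal at clinical discretion make some difference possible, but nothing in the protocol predicts one. Equality is also not exact once the 48-hour tail is kept: HR 0.80 with dwell 1.25 times as long gives 19.1% v 18.6%.

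Nor does section 17 say that the economic model would take its BSI risk from a Kaplan-Meier curve.

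**Conclusion.** The point holds for the display. Following sections 9.6, 4.1, 8.2 and 8.3 as written, most babies are censored at a competing event, and one minus Kaplan-Meier overstates the proportion with a BSI. Under the protocol's rate and median dwell the excess is about 2 percentage points at day 10, 9 at day 20 and 17 at day 30. These sizes rest on a constant hazard, exponential dwell and removal independent of BSI. Across the quoted range of mean dwell the day-30 ratio runs from about 1.5 to 2.4.

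The primary p-value and the sample size are unaffected. Disagreement between the log-rank result and the proportions infected is a possibility that the report should be able to show, not a forecast.

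For time to full milk feeds the same reasoning applies with death as the competing event. Its size cannot be computed, because the protocol gives no death rate for this population. The infant mortality of 144 per 1000 very preterm live births in section 2.1 is background only, but suggests that deaths will not be negligible.

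This is an improvement that should be made; it does not invalidate the primary analysis.

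**What to change.** In section 9.6, and then in the SAP:

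1. Keep the log-rank test as the primary test, and describe it as a comparison of the BSI rate while the line is in place.
2. Display first BSI with cumulative incidence (Aalen-Johansen) curves by arm, with end of line exposure (removal plus 48 hours) and death as competing events. Babies lost through transfer remain ordinary censored observations.
3. Report the between-arm difference in cumulative incidence with a 95% CI, at a time point named in advance, and read it alongside the occurrence of one or more BSI and time to PICC removal.
4. For time to full milk feeds, use cumulative incidence with death as a competing event. Kaplan-Meier remains suitable for time to death.

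The cost is a few sentences and standard software. Removal dates (Form 6) and deaths (Form 7a) are already collected, so no extra data or babies are needed, and the power of the primary test does not change.
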